5.7.1.2. Primary Analysis

The hypothesis testing for the primary endpoint will be tested comparing each lumasiran group to the placebo group during the 6-month primary analysis period in the FAS with a 2-sided significance level of 0.05.

The primary endpoint will be analyzed using an MMRM approach using the ICE strategy described in Table 2. The outcome variable is percent change from baseline in 24-hour urinary oxalate to Month 6. The model includes baseline 24-hour urinary oxalate (as defined in Section 4.4) and the stratification factor of number of historical kidney stone events (≤ 1 versus >1 event in the 12 months prior to screening) as covariates, and fixed effect terms including treatment arm (lumasiran 567 mg or lumasiran 284 mg vs placebo), visit (Months 3, 4, 5, 6) and treatment-by-visit interaction. The primary treatment effect estimate from this model will represent the average percent change from baseline in 24-hour urinary oxalate across months 4 through 6, which is calculated via a linear contrast of the corresponding coefficients from the MMRM model. An unstructured covariance structure matrix fails to converge, then the following covariance structure will be assessed in this order: autoregressive (1), compound symmetry, Toeplitz. The Satterthwaite approximation will be used to estimate the denominator degrees of freedom.

The LS mean, standard error of the mean (SEM), 95% confidence interval (CI), and p-value will be generated for each treatment arm and the treatment difference between each lumasiran dose

and placebo from Months 4 through 6. In addition, the LS means, SEM, and 95% CI will also be generated for each visit (Months 3, 4, 5, 6) by treatment arm.

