2.4. Randomization Methodology

Patients will be randomized 1:1:1 to receive lumasiran 284 mg, lumasiran 567 mg, or placebo in a DB manner. Stratification will be performed at randomization according to baseline urinary oxalate level ($\leq 1.25 \times ULN \text{ vs} > 1.25 \times ULN$) from the mean of the first 2 valid 24-hour urine collections and the number of historical kidney stone events in the 12 months prior to screening ($\leq 1 \text{ vs} > 1$).

For stratification, a historical kidney stone event is defined as:

- the visible passage of a kidney stone
- a procedural intervention for removal of an asymptomatic or symptomatic stone

- if more than 1 stone was removed in a given procedure, this counts as 1 event unless bilateral ureteral stones were removed, in which case this counts as 2 events
- if more than 1 procedure was required to remove a single stone, this counts as 1 event
- a new (≥1 mm) or enlarged (by ≥2 mm) kidney stone on computed tomography (CT) imaging
 - it must be evident from the CT scans that the new or enlarged kidney stone event occurred during the 12 months prior to screening
 - if a procedure was performed to remove the stone(s) identified by CT, then only the procedure will be counted to avoid double counting the same stone.

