2.6. Determination of Sample Size

The planned enrollment for this study is 120 patients.

The study is powered to detect a difference in urinary oxalate excretion between each lumasiran group and the placebo group. Assuming a standard deviation of 45% in the percent change from baseline in 24-hour urinary oxalate levels at Month 6, a sample size of 40 patients per group will enable a power of at least 80% in detecting a treatment difference of 30% between the treatment groups at a 2-sided significance level of 0.05. Table 1 shows the statistical power under various assumptions for a sample size of 40 per group.

Assumed standard deviation (SD)	Assumed difference (lumasiran – placebo)	Power
250/	20%	94%
2370	30%	99%
200/	20%	84%
50%	30%	99%
450/	20%	50%
4.370	30%	84%

Table 1: Sample Size Power Calculation	Table 1:	Sample Size Power Calculation	ons
--	----------	-------------------------------	-----

Abbreviations: SD=standard deviation

No multiplicity adjustment is considered in the sample size calculation.

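### Minor: if the unstructured covariance fails, the SAP tries AR(1) before the more general Toeplitz, which could understate the standard error of the primary contrast

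*SAP*

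**What the plan says.** SAP 5.7.1.2 analyses percent change in 24-hour urinary oxalate with an MMRM containing "visit (Months 3, 4, 5, 6) and treatment-by-visit interaction". The tested quantity is the Months 4 to 6 average, "which is calculated via a linear contrast of the corresponding coefficients from the MMRM model". Each lumasiran dose is compared with placebo "with a 2-sided significance level of 0.05".

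The first-choice covariance is unstructured. The sentence that sets the trigger for the fallback has no conditional opening in the text available. It begins "An unstructured covariance structure matrix fails to converge" and goes on to say that "the following covariance structure will be assessed in this order: autoregressive (1), compound symmetry, Toeplitz". The sense is clear, but the wording is incomplete. The SAP does not say whether the first structure to converge is kept or whether the structures are compared.

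Degrees of freedom are Satterthwaite. No robust standard error and no information criterion is named. The only sensitivity analysis of the primary endpoint (SAP 5.7.1.3) concerns vitamin C. Protocol 7.2.5 describes the same model without a covariance structure. SAP 5.7.1.4 and 5.7.2 reuse the model for absolute change in oxalate and for calcium oxalate supersaturation.

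**The concern.** AR(1) and compound symmetry are each special cases of Toeplitz. A two-parameter AR(1) on four equally spaced visits will rarely fail to converge. If the first converging structure is kept, Toeplitz is therefore listed but does almost no work.

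AR(1) makes correlation decay geometrically with lag. Repeated percent changes in one patient share a baseline denominator, and patients are asked to keep a stable prophylaxis regimen and a consistent diet (Protocol 4.1 and 5.6.3). Correlation may therefore persist across visits more than AR(1) allows. The model would then understate the variance of a three-visit average. Confidence intervals would be too narrow and p-values too small, with no robust standard error to catch it.

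The unstated selection rule adds a smaller problem. SAP 2.5 has the sponsor unblinded throughout, so the choice of covariance should leave no discretion.

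**Working it through.** **1. The plan's own figure.** From SAP 2.6: 40 per arm, SD 45%, difference 30 percentage points, two-sided 0.05. SE = 45 × √(2/40) = 10.06. Then 30/10.06 = 2.98, and power = Φ(2.98 − 1.96) = 84.7% (83.8% with the noncentral t on 78 df). Table 1 states 84%. All six entries reproduce within 2 points. The calculation contains no within-patient correlation, so it says nothing about the covariance.

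**2. Size of each structure at 4 visits.** Unstructured: 4 × 5/2 = 10 parameters. Heterogeneous Toeplitz: 4 variances + 3 correlations = 7. Toeplitz: 1 + 3 = 4. AR(1) and compound symmetry: 2 each.

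**3. AR(1) fitted when the truth is compound symmetry.** The inputs are weights (0, 1/3, 1/3, 1/3), visits on Days 85, 113, 141 and 169 (28 days apart, Protocol Table 1), equal variances and complete data, with covariates ignored. The documents give no correlation, so ρ is assumed and varied. In large samples the fitted AR(1) parameter equals the true ρ. Per unit variance:

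- true variance of the average: (3 + 6ρ)/9
- variance under AR(1): (3 + 4ρ + 2ρ²)/9
- SE ratio: k = √[(3 + 4ρ + 2ρ²)/(3 + 6ρ)]
- type I error: 2 × [1 − Φ(1.96k)]

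| ρ | k² | k | Type I error |
|---|---|---|---|
| 0.10 | 3.42/3.60 | 0.975 | 5.6% |
| 0.30 | 4.38/4.80 | 0.955 | 6.1% |
| 0.37 | 4.7538/5.22 | 0.954 | 6.14% (maximum) |
| 0.50 | 5.50/6.00 | 0.957 | 6.06% |
| 0.70 | 6.78/7.20 | 0.970 | 5.7% |
| 0.90 | 8.22/8.40 | 0.989 | 5.25% |

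At the maximum the SE is 1 − 0.954 = 4.6% too small. A search over equal-variance Toeplitz truths with non-negative, non-increasing correlations gave the same maximum.

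**4. Simulation** (3 arms of 40, complete data, 6,000 trials, two comparisons each, Monte Carlo error about 0.2 points).

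| Truth | AR(1) fitted | Compound symmetry fitted | Toeplitz fitted |
|---|---|---|---|
| Compound symmetry 0.3 | 6.3% | 5.2% | 5.1% |
| Compound symmetry 0.5 | 5.8% | 4.8% | 4.7% |
| Compound symmetry 0.7 | 5.8% | 5.0% | 5.0% |
| AR(1) 0.5 | 5.05% | 5.9% | 4.95% |

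The last row shows that moving compound symmetry to the front would only exchange one misfit for another. Toeplitz is close to nominal in all four rows.

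**5. Other equal-variance truths, AR(1) fitted.** A random intercept plus AR(1) gives 5.1% to 5.6%. Correlations that fall faster than AR(1) make the SE too large, with type I error down to about 3.8%.

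**6. Unequal variances, AR(1) fitted.** Take compound symmetry 0.5. Relative SDs of 0.7/1.0/1.1/1.2 at Months 3 to 6 give 8.7%; 1.3/1.0/1.0/1.0 give 3.8%. Plain Toeplitz also assumes equal variances, so it would not correct this. Heterogeneous Toeplitz lets the variances differ.

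**7. How often the fallback would be used.** REML unstructured fits to simulated Gaussian data, 3 arms of 40, converged in 200 of 200 runs in each of three settings: 10% of visits missing with ρ 0.5, 30% missing with ρ 0.5, and 30% missing with ρ 0.8. The data were well behaved and the software was not SAS, so failure is not excluded. With an assumed 2% chance of failure and the equal-variance worst case, overall type I error is 0.98 × 5% + 0.02 × 6.1% = 5.02%.

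**The case against.** The strongest reply is that the fallback will almost certainly not be used. Ten covariance parameters with about 120 patients is an easy problem, and step 7 puts the overall effect at a few hundredths of a percentage point. That stands for the main analysis and is why the point is minor. It is weaker for subgroups: SAP 5.7.4 allows model-based estimates with as few as 10 patients in an arm. The SAP does not say that the same MMRM is used there.

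A second reply is that the direction is assumed. A reader might infer that the fallback would make the standard errors too small. The documents do not support that, because they give neither within-patient correlations nor by-visit variances. The design also offers a reason why correlation may not be constant: a dose follows the Month 3 collection, and Protocol 3.3 predicts near-steady state only at Month 6. This stands, so the claim is that the order could understate the SE.

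Third, a reader might take 6.1% as a ceiling on the error. It is not, as step 6 shows.

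Fourth, the SAP says that the structures are assessed in order, not that the first to converge wins. Keeping the first is the natural reading, but it is not explicit.

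Finally, this is a Phase 2 study that tests two doses at 0.05 each without multiplicity adjustment. An SE error of a few percent in an unlikely branch changes little against a planned 30-point difference.

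**Conclusion.** The point holds as a minor specification matter. If the unstructured fit fails, if the first converging structure is kept, and if correlation persists more than AR(1) allows, the SE of the Months 4 to 6 average could be understated by up to about 4.6%, with type I error up to about 6.1% per comparison. Those maxima rest on equal variances, non-negative and non-increasing correlations, equally spaced visits and complete data. With equal variances and a true AR(1) there is no error, and with faster decay the test is conservative. The plan does not, on this evidence, carry a 6.1% type I error for its primary test: the trigger is unlikely and the correlation pattern unknown. A fallback should still not introduce a bias that reordering the list would avoid.

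**What to change.** Amend the sentence in SAP 5.7.1.2 before database lock:

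- Restore the conditional opening, for example: *If an unstructured covariance matrix fails to converge*.
- Order the fallbacks from general to simple: heterogeneous Toeplitz, Toeplitz, then compound symmetry or AR(1).
- State that the first structure to converge is kept.

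A sandwich standard error with a structured fallback is optional. Uncorrected, it is itself mildly anti-conservative at this sample size: simulated type I error was 5.6% at ρ 0.3 and 5.4% at ρ 0.6, with an AR(1) working matrix and true compound symmetry. It should be used only with a named small-sample correction and compatible degrees of freedom, since the SAP specifies Satterthwaite.

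The cost is a small edit to the SAP. The downside is that a more general fallback may itself fail to converge, in which case the analysis passes to the next structure on the list.

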5.7.1.3. Sensitivity Analyses

A sensitivity analysis will be conducted including all data without censoring assessments after the initiation of select vitamin C equivalent medications.

5.7.1.4. Other Analyses

Descriptive statistics will also be generated for the actual values, change from baseline, and percent change from baseline at each scheduled visit by treatment arm. LS Mean (+/- SEM) figures of percent reduction by treatment arm will be plotted as well as individual spaghetti plots. Listings will also be generated.

The exploratory endpoint of absolute change in 24-hour urinary oxalate from baseline to Month 6 (average across Months 4 through 6) will be analyzed using the MMRM model specified for the primary endpoint.

5.7.2. Secondary Endpoints

The percentage of patients who achieve a $\geq 20\%$ reduction in 24-hour urinary oxalate from baseline to Month 6 (average across Months 4 through 6) will be analyzed using the Cochran-Mantel-Haenszel (CMH) test stratified by the 2 stratification factors (Section 4.5). The odds ratio with the corresponding 95% CI and associated p-value will be presented. In addition, the differences in proportion of responders and corresponding 95% CI using the Newcombe method based on the Wilson score will also be presented. In addition, a tabulation and a bar chart showing the proportion of patients with a $\geq 20\%$ reduction in 24-hour urinary oxalate from baseline to each visit and on average across Months 4 through 6 will be presented.

For the analysis of urinary calcium oxalate, selected medication could potentially impact the endpoint, therefore the assessments will be excluded from analysis if patients start, stop, or change any of the following medications within a specified time frame of the data collection:

- Vitamin C equivalent to ≥500 mg in a single day is taken at any point within 4 days prior to the start of or during the urine collection (see Table 2)
- The patient is on a new daily dose (relative to screening) of hydrochlorothiazide, allopurinol, topiramate, acetazolamide or furosemide at any point within 4 days prior to the start of or during the collection
- Urine alkalinization agents (potassium citrate, potassium citrate-citric acid, sodium citrate-citric acid, sodium citrate-potassium citrate-citric acid, sodium bicarbonate, potassium bicarbonate, or potassium bicarbonate-potassium citrate) started, stopped, or changed at any point within 2 days prior to the start of or during the collection (relative to screening)

Percent change in urinary calcium oxalate supersaturation from baseline to Month 6 (average across Months 4 through 6) will be analyzed using the same MMRM approach as for the primary endpoint. Descriptive statistics will also be generated for the actual values, change from baseline, and percent change from baseline at each scheduled visit by treatment arm. LS Mean (+/- SEM)

figures of percent reduction by treatment arm will be plotted as well as individual spaghetti plots. Listings will also be generated.

A sensitivity analysis of the percent change in urinary calcium oxalate supersaturation from baseline to Month 6 (average across Months 4 through 6) will also be analyzed using the same approach as the main analysis above including all data without excluding assessments that could potentially be impacted by selected mediations.

5.7.3. Exploratory Endpoints

Apart from the 24-hr urinary oxalate, all other exploratory endpoints will be by treatment arm (lumasiran 567 mg, lumasiran 284 mg, placebo) during the 6-month primary analysis period using the FAS. These endpoints will also be summarized for the 15-month DB period by treatment arm using the FAS. The change from baseline in 24-hr urinary oxalate will be summarized after Month 6. Listings will also be generated for each exploratory endpoint below.

5.7.3.1. Kidney Stone Events

CT scans for radiographic kidney stone events are read in pairs blinded to visit date (baseline and Month 15). All kidney stone-related analyses in this section will be done with all data collected.

A clinical kidney stone event is defined as one of the following:

- Visible passage of a kidney stone
- A procedural intervention for removal of an asymptomatic or symptomatic stone (information on the location, number, and size of stones removed will be collected)
- Or, in the case of potential stone passages without visible stones, it will be up to the Investigator to evaluate patients' symptoms and determine whether a stone passage occurred or the symptoms were due to a different cause.

A radiographic kidney stone event is defined as a kidney stone that is increased in size by $\geq 2 \text{ mm}$ in at least one dimension or a new stone ($\geq 1 \text{ mm}$ in size) observed on CT at Month 15 relative to baseline.

Time to first kidney stone event

Time to first event is defined as date of the first study drug to the first date of a kidney stone event. Censoring applies to patients who do not have a kidney stone event during the study. The follow-up time of these patients will be censored at the lost to follow-up date, study discontinuation, data cut-off date, or end of study, whichever occurs first.

Time to the first kidney stone event will be analyzed for a combination of both clinical and radiographic kidney stone events and for clinical kidney stone events separately for both the 6-month primary analysis period and the 15-month DB period (FA). All available data at the time of each database lock will be used. Kaplan-Meier estimator will be used to estimate the distribution of time to first kidney stone event in each treatment group. A log-rank test will be used to evaluate the treatment differences between each dose and the placebo. In addition, Cox proportional hazard regression will be performed to estimate the hazard ratio along with the 95% CI and p-value for each dose compared to the placebo. The model includes treatment, number of historical kidney stone events (>1 versus \leq 1) in the 12 months prior to screening.

Incidence rate of clinical and radiological kidney stone events

The incidence rate of kidney stone events will be analyzed for a combination of both clinical and radiographic kidney stone events and for clinical kidney stone events separately for both the 6-month primary analysis period and the 15-month DB period (FA).

The incidence rate will be calculated as the total number of kidney stone events divided by total person-years at risk during the respective period (ie, 6-month primary analysis period and 15-month DB period). Years at risk is defined as (time from first lumasiran dose until 168 days after the last dose of lumasiran, lost to follow-up date, study discontinuation, data cut-off date, or end of study, whichever occurs first)/365.25.

The endpoint will be analyzed using a negative binomial regression model that include fixed effects of the treatment arm and the number of historical kidney stone events (>1 versus \leq 1) in the 12 months prior to screening. The logarithm of the follow-up time of each patient will be included in the model as an offset variable. The p value and the ratio of mean kidney stone event rate between two treatment arms with the corresponding 95% CI will be estimated.

The total number of patients with at least one kidney stone event, total number of kidney stone events, total number of person-years will be presented. Descriptive statistics for the median and interquartile range of the kidney stone event rate will also be presented by treatment arm.

Other radiographic assessments

Change from baseline in radiographic assessments of kidney stones (eg stone volume) will be summarized descriptively.

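### The composite time-to-first-stone analysis treats an interval-censored CT finding as an exactly dated event, so its Kaplan-Meier curve misleads; separately, optional CT lowers the absolute composite rate (minor, exploratory)

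*SAP*

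**What the plan says.** SAP 5.7.3.1 plans the stone analyses twice over: time to first "event will be analyzed for a combination of both clinical and radiographic kidney stone events and for clinical kidney stone events separately for both" analysis periods (6 and 15 months). The incidence rate follows the same pattern.

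- **Radiographic event.** Growth of at least 2 mm, or a new stone of at least 1 mm, "observed on CT at Month 15 relative to baseline".
- **Time to event.** Time runs from the "date of the first study drug to the first date of a kidney stone event". For patients without an event, "The follow-up time of these patients will be censored at the lost to follow-up date, study discontinuation, data cut-off date, or end of study", whichever is earliest. The methods are Kaplan-Meier, log-rank and Cox. No interval-censored method is named, and the date rules in SAP 7.3 cover only medications and adverse events.
- **Data used.** "All kidney stone-related analyses in this section will be done with all data collected", and for time to event, "All available data at the time of each database lock will be used". SAP 4.6 instead limits the efficacy summaries at the primary analysis to data through the Month 6 visit.
- **Incidence rate.** Events are divided by person-years within the period. Risk time is the "time from first lumasiran dose until 168 days after the last dose of lumasiran", or an earlier end of follow-up. In the negative binomial model, "The logarithm of the follow-up time of each patient will be included in the model as an offset variable".
- **CT schedule.** Protocol 6.2.2.2 and Table 1 footnote d make CT optional, at baseline and Month 15. A scan at early termination is discretionary and only after Month 6. SAP 7.1 reproduces an earlier schedule with CT for all patients. SAP 5.7.3 uses the FAS, and no paired-CT set is defined.

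**The concern.** A pair of scans 15 months apart shows that a stone appeared or grew, but not when. Kaplan-Meier and Cox need to know when. If the event takes the scan date, two things follow. Before the Month 15 window the composite curve contains no scheduled radiographic event, so it repeats the clinical-only curve under a composite label. Inside the window each radiographic event falls on the patient's own last day of follow-up, alongside the censoring of event-free patients, and the curve drops sharply as the risk set empties.

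The rate has a different problem. A patient without a CT pair adds person-years but cannot contribute a radiographic event, so the absolute composite rate depends on CT uptake.

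At stake are the descriptive stone results: the curve, any median, and the absolute rate. Protocol 3.2 gives stone-event data as one reason for continuing to Month 15, so these results are likely to be read.

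**Working it through.** The documents give no stone rate, CT uptake, enrolment pace or power for stone events, so there is no planned figure to reproduce. All rates below are assumptions.

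**1. Timing (from the documents).** Month 15 is Day 421 ± 28, that is Days 393 to 449. Apart from a discretionary early-termination scan, no radiographic event can be observed before Day 393.

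**2. Composite curve.** Assumed: clinical hazard 0.2/365.25 = 0.000548 per day; 40% radiographic risk by Day 421, so hazard −ln(0.6)/421 = 0.001213 per day; 40 per arm; full CT uptake; visits uniform over the window.

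- Reference (constant-hazard onset): exp(−(0.000548 + 0.001213) × day).
- What the curve shows before Day 393: exp(−0.000548 × day).
- From Day 393 on: simulation with scan-date events.

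| Day | Composite curve | Reference | At risk of 40 |
|---|---|---|---|
| 169 | 91% | 74% | 36 |
| 253 | 87% | 64% | 35 |
| 392 | 81% | 50% | 32 |
| 421 | 60–61% | 48% | 16 |
| 430 | 51–52% | 47% | 11 |
| 440 | 38% | 46% | 5 |
| 449 | 12–13% | 45% | almost none |

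If every scan falls exactly on Day 421, the value there is 0.794 × 0.60 = 0.476. This equals the reference, so only the earlier shape is wrong. With 20% radiographic risk and spread visits, the curve reads 81% at Day 392 (reference 65%) and 33% at Day 449 (reference 62%).

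**3. Absolute composite rate.** Factor = (c + u × r)/(c + r), where c is the clinical rate, r the radiographic rate and u the CT uptake. At u = 0.5:

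- c = 0.2, r = 0.4: (0.2 + 0.2)/0.6 = 0.67.
- c = 0.4, r = 0.2: (0.4 + 0.1)/0.6 = 0.83.

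**4. Arm comparison.**

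- Simulated log-rank type I error (40,000 trials per setting): 5.2% at full uptake, 5.0% at 50%/50%, 5.6% at 60%/50%, 10.3% at 70%/40%.
- With equal underlying uptake of 30% to 70%, a gap of 30 points or more arises by chance in 0.5% to 1.0% of trials.
- A true hazard ratio of 0.60 on both components gives a composite Cox estimate of 0.64 at full uptake and 0.63 at 50%.
- The rate ratio stays 0.60 if both components respond equally. If only radiographic events respond (c = 0.2, r = 0.4), it is (0.2 + 0.24)/0.6 = 0.73 at full uptake and (0.2 + 0.12)/0.4 = 0.80 at 50%.

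**5. The 6-month lock.** Under SAP 4.6, the 6-month composite almost duplicates the clinical-only analysis. Under SAP 5.7.3.1, it can add Month 15 scans from early enrollees. With uniform enrolment over E months, the share past Month 15 when the last patient reaches Month 6 is (E − 252/30.44)/E: 31% for E = 12 and 54% for E = 18. At 50% uptake, 16% or 27% of patients could contribute a scan.

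**6. Risk time.** An on-schedule Month 9 dose gives Day 253 + 168 = Day 421, while the Month 15 visit may be as late as Day 449. With both visits uniform in their windows, the Month 15 visit falls after risk time ends in about half of patients, by 9 days on average over all patients: 9/420, about 2%.

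**The case against.** **The natural reading dates the event at the scan, so nothing is missing.** The event definition does point to the scan date. A reader might infer that the absent dating rule is the cause and that writing one would cure it. It would not: every scan-dated figure above already assumes that rule. The cause is a single post-baseline CT combined with an estimator for exactly dated events.

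**The collapse at Day 449 is a tail artefact.** This largely stands. At Day 430, with about 11 at risk, the curve is within about 5 points of the reference; below it, few remain. The clearer fault is the long stretch before Day 393.

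**The reference curve is assumed.** Fair. It is latent onset at constant hazard, and the SAP defines no radiographic status before Month 15. That is itself a reason not to draw a composite curve over those months.

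**Optional CT is version lag.** Also fair. The SAP carries the schedule from before CT became optional. That explains the mismatch without removing it.

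**The rate's numerator and denominator may already match.** A reader might infer from "All kidney stone-related analyses in this section will be done with all data collected" that events after risk time ends are still counted. A patient dosed only on Day 1 and followed to Month 9 under Protocol 4.3.1 would then have 252 days of events over 168 days at risk, a factor of 1.5. The phrase may instead contrast with the medication-based exclusions in SAP 5.7.2, and the rate is defined within a period. Even on the wider reading, if 10% of an arm did this, the factor would be (0.9 × 420 + 0.1 × 252)/(0.9 × 420 + 0.1 × 168) = 1.02. Naming lumasiran rather than study drug looks like a drafting slip: SAP 5.5 uses study drug with the same 168 days.

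**The FAS comparison preserves randomisation.** This stands. Restricting the whole composite to paired-CT patients would condition on Month 15 completion and drop clinical events in unscanned patients.

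**Conclusion.** The concern holds as a minor point. As written, the composite Kaplan-Meier curve understates stones before Month 15 by an amount set by the radiographic risk: 81% against 50% event-free at Day 392 at an assumed 40% risk, or 81% against 65% at 20%. It then falls too far late in the window if visits are spread. The absolute composite rate is too low when uptake is partial, by a factor of 0.67 to 0.83 at an assumed 50%.

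Two stronger conclusions are not supported. A reader might infer that the treatment comparison is invalid. With balanced uptake, type I error stays near 5% and attenuation is small; a large imbalance would matter, but it is unlikely while sites and patients are blinded (Protocol 3.5). A reader might also infer that the rate is free of dating questions. It is not, because assigning an event to the 6-month or 15-month period needs a date.

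The clinical-only analyses avoid the CT problem, but they share the conflict over data at the 6-month lock and the risk-time wording. Everything here is exploratory; no primary or secondary result changes.

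**What to change.** Amend the SAP as follows:

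- Make the planned clinical-only analysis the time-to-event result.
- Replace the composite Kaplan-Meier, log-rank and Cox with an interval-censored analysis, or report radiographic events as the number and proportion by Month 15 among patients with paired CT, by arm. Show CT completion by arm in either case.
- Keep clinical events for all FAS patients; do not restrict them to the paired-CT subset.
- Drop the 6-month composite, and reconcile SAP 4.6 with 5.7.3.1 on the data used at the 6-month lock, for the clinical-only analysis too.
- Define years at risk by study drug in all arms, and count events over the same window as exposure.
- State whether an early-termination CT can count as a radiographic event.
- Align the SAP with Protocol Amendment 2 and record the change in SAP Section 6.

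The cost is a SAP amendment, with no new data. The radiographic result will rest on a smaller, self-selected subset. At an assumed 40% event proportion, the 95% half-width for an arm difference is 1.96 × √(2 × 0.4 × 0.6/n): about 21 points with 40 per arm and 30 points with 20 per arm (50% uptake). The subset may also differ between arms in who completes Month 15, which is why completion must be shown.
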